### 10.3 Analysis Datasets

All patients with full study protocol participation are included in the analysis dataset, i.e. with results on both measurements, the subjective device (HemoPill acute capsule) and the control product (endoscopy). Therefore, only patient withdrawal or termination by the investigator can lead to exclusion from the analysis dataset (described in detail in section 5.7).

No further (sub-)analysis datasets are planned.

---

## 10.4 Description of Statistical Methods

### 10.4.1 General Approach

This study has a double blinded, prospective diagnostic case-control design. This prototypic design of diagnostic accuracy study is a consecutive series of individuals in whom the target condition is suspected, here GI lumen bleeding. The index test, here HemoPill acute, is performed first in all participants. Subsequently, the presence of the target condition is also measured in all participants with the reference standard, in this case endoscopy (Rutjes et al. 2005).

In more detail, this study is performed:

- on one sample: the study is conducted on a single sample (single-arm) at a single center
- double blinded: neither the patients nor the investigators are aware of the result of the subjective device, the HemoPill acute capsule, during the examination of the control product, the endoscopy.
- with repeated measurement: all patients are measured with the subjective device and additionally with the control product
- case-control design: the status of a patient with positive endoscopy result equals as classification in the case group, the status of a patient with negative endoscopy result equals as classification in the control group. This classification is determined after the study process, during the statistical analysis to ensure double blindness.

The categorical variables (such as positive or negative test results) will be summarized with subject counts, respectively frequency, and percentages.

As inferential test a  $\chi^2$  test, goodness-of-fit test of a 2 x 2 contingency table with two tailed p-value of  $\alpha \leq .05$  will be used.

The assumption of the  $\chi^2$  test, goodness-of-fit test, a required minimal expected cell size of 5, will be controlled (and is a priori controlled in the power analysis, see section 10.5). The dichotomous data level of the two factors, results of subjective device and results of control product, are transformed into a cell count, observed cases, in the 2 x 2 contingency table.

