### 10.2 Statistical Hypotheses

Formal hypotheses are only specified for the primary clinical effectiveness endpoint, the detection of blood in the gastrointestinal lumen with both measurements.

The assumed null hypothesis is that the accuracy of the HemoPill acute measurement in comparison with endoscopic finding is 50%, equaling a random distribution and no relation between these measurements. As the alternative hypothesis, it is assumed that the accuracy is equal or higher to 75%. This concrete accuracy value is derived from previous results of Brunk et al. (2021), see section 2.1.

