### 10.4.2 Analysis of the Primary Efficacy Endpoint(s)

The original continues data level of the subject device, HemoPill acute, the so-called HI-value, is transformed during the study process by the investigator in dichotomous values, negative or positive for GI lumen bleeding, i.e. negative or positive output results (described in detail in section 2.1.2.2).

The qualitative visual data of the control product, the endoscopy, is also transformed during the study process by the investigator in dichotomous values, negative or positive for GI lumen bleeding, i.e. negative or positive output results (described in section 4.1).

After the study process the values of these two factors (HemoPill acute: negative or positive, endoscopy: negative or positive) are combined in a 2 x 2 contingency table with four possible results:

- True positive: HemoPill acute measurement positive; Endoscopy measurement positive
- False positive: HemoPill acute measurement positive; Endoscopy measurement negative
- True negative: HemoPill acute measurement negative; Endoscopy measurement negative
- False negative: HemoPill acute measurement negative; Endoscopy measurement positive

(for detailed description see section 4.1)

From this 2 x 2 contingency table the summary three test indices are calculated accuracy (ACC, = (TP + TN) / pop), sensitivity (true positive rate) and specificity (true negative rate).

The significance of these results will be analyzed using the  $\chi^2$  test, goodness-of-fit test of a 2 x 2 contingency table with two tailed p-value of  $\alpha \leq .05$ .

The data assumption of the  $\chi^2$  test, goodness-of-fit test, a required minimal expected cell size of 5, will be controlled. After the inference analysis the 95% confidence intervals of the test indices can be calculated. If either of both measurement results is missing for a patient, the whole subject is omitted from the data analysis.

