## 10.5 Sample Size

The study will enroll in total n = 50 participants:

- at least 43 eligible for statistical analyses
- plus 7 as highest expectable dropout count.

The required sample size of n = 43 was calculated for the planned  $\chi^2$  test for the test indices (accuracy, sensitivity and specificity). The calculation was based on the previous clinical study of Burk et al. (2021) which provide an accuracy of 75% (sensitivity of 100% and specificity of 63%) equaling an assumed effect size  $w = 0.62$ . The calculation was done with an a priori set  $\alpha$  error of .05 and a targeted power (1- $\beta$ ) equal or higher than .90.

Based on the previous studies dropout ratios between 2% (Burk et al., 2021) and 7% (Caca & Zimmermann, 2017) could be expected. By reason of clinical judgement, a maximal dropout ratio of 14% was assumed (which equals two times the maximal previous dropout ratio). An assumed maximal dropout of 14% equals 7 additional participants (when targeting at least 43 participants eligible for statistical analyses).

The targeted n = 43 also assures the required minimal expected cell size of 5 for a  $\chi^2$  test being applicable. The method of power analysis was an a priori required sample size computation with given  $\alpha$ , power and effect size. The power analysis was conducted with the computer program G\*Power 3.1 (Faul et al., 2009).

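### The sample size of 43 does not follow from the effect size, alpha and power printed in section 10.5, and the primary test is given no null, degrees of freedom or direction

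*Combined protocol and SAP*

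**What the plan says.** Section 10.2 takes as null an accuracy of 50% against endoscopy. Of the alternative it says: "As the alternative hypothesis, it is assumed that the accuracy is equal or higher to 75"%. That is a hypothesis about one proportion, and it points one way.

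Section 10.4.1 sets the inferential rule as a chi-square "test, goodness-of-fit test of a 2 x 2 contingency table with two tailed p-value of" .05. Section 10.4.2 describes the data as capsule and endoscopy results that "are combined in a 2 x 2 contingency table with four possible results", from which accuracy, sensitivity and specificity are calculated. It continues "The significance of these results will be analyzed using the" chi-square test, again as a "goodness-of-fit test of a 2 x 2 contingency table with two tailed p-value of" .05. Neither section gives the cell proportions expected under the null, the degrees of freedom, or a condition on the direction of the result.

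Section 10.5 states that the earlier multicentre series would "provide an accuracy of 75% (sensitivity of 100% and specificity of 63%) equaling an assumed effect size" of w = 0.62. It gives alpha as .05 and power as "equal or higher than .90", and arrives at 43 evaluable patients, raised to 50 for dropout. It describes the method as an a priori computation of the required sample size from given alpha, power and effect size. Section 10.1 says that there is no separate SAP.

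**The concern.** With no separate SAP, these few sentences are the whole decision rule for the primary endpoint. Two things do not fit.

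First, a sample size computed from a stated effect size, alpha and power should be recoverable from them once the degrees of freedom are known. Here no ordinary choice of degrees of freedom recovers 43, so at least one printed input appears not to be the one used.

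Second, a chi-square goodness-of-fit test on four cells and one on correct against incorrect are different tests with different nulls. The plan does not say which is meant. Either responds to departure from the null in any direction, whereas the claim in section 10.2 is that accuracy is high. If the test, its null and its direction are settled only at analysis, they could be settled after the capsule results have been compared with endoscopy.

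**Working it through.** **Inputs.** w = 0.62, alpha .05, power at least .90, n = 43 (section 10.5). Null accuracy 50%, alternative 75% (section 10.2). Earlier series (section 2.1): 35 capsule-positive patients, 20 of them with bleeding at endoscopy, and 25 capsule-negative patients, of 60. Degrees of freedom are not stated.

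**Formulas.** Effect size w = √Σ[(p1 − p0)²/p0]. Power is the probability that a noncentral chi-square with λ = n·w² exceeds the upper-tail critical value at alpha. Required n is the smallest n with power of at least .90.

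**Step 1: section 10.5 as printed, w = 0.62.**

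| df | n at alpha .05 | n at alpha .025 |
|---|---|---|
| 1 | 28 | 33 |
| 2 | 33 | 39 |
| 3 | 37 | 43 (power .902) |

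At the printed alpha of .05 the answer is never 43.

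**Step 2: where w = 0.62 comes from.** Counting all 25 capsule-negative patients as true negatives, the series gives TP/FP/TN/FN = 20/15/25/0. Accuracy is 45/60 = 75%, sensitivity 20/20 = 100% and specificity 25/40 = 62.5%, which match section 10.5. Against 25% per cell:

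w² = (.333 − .25)²/.25 + (.25 − .25)²/.25 + (.417 − .25)²/.25 + (0 − .25)²/.25 = .028 + 0 + .111 + .25 = .389, so w = 0.624.

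The printed w therefore fits a null of four equal cells with 3 df. At n = 43, λ = 43 × 0.62² = 16.53. Power is .942 at alpha .05 and .902 at alpha .025. The smallest n is 37 at .05 and 43 at .025.

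**Step 3: the section 10.2 hypothesis.** For correct against incorrect, w² = (.75 − .50)²/.50 + (.25 − .50)²/.50 = .125 + .125 = .25, so w = 0.50 with 1 df. At n = 43, λ = 43 × .25 = 10.75. At alpha .05 power is .906, and 43 is the smallest n that reaches .90.

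So 43 is reproduced by two routes. One keeps the printed w and needs alpha .025; the other keeps the printed alpha and needs w = 0.50.

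**Step 4: direction.** On the 1-df test with 43 patients the expected count is 21.5 in each category, and chi-square = 2 × (correct − 21.5)²/21.5.

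- 28/43 (65.1%): 2 × 6.5²/21.5 = 3.93, p = .047
- 15/43 (34.9%): 2 × 6.5²/21.5 = 3.93, p = .047

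Both pass .05 as the rule is written.

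**Step 5: does the choice of test matter?** For 28/43 the 1-df chi-square gives p = .047 and the exact two-sided binomial test gives p = .066. On four equal cells, 28 correct does not fix a p-value: with the correct results split 14/14 and the incorrect 8/7, p = .26; with 12/16 and 15/0, p = .0017.

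**Step 6: dropout.** 43/(1 − .14) = 50, as stated.

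**The case against.** Four points can be made for the plan.

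- **Alpha is not contradicted.** The text says .05 in sections 10.4.1, 10.4.2 and 10.5, and .025 is printed nowhere for this test. This stands. A reader might infer that two alphas compete to decide the trial and that 28/43 correct is significant or not depending on which applies. The documents do not support that. The .025 is an inference that also needs 3 df and four equal cells, while the p = .047 for 28/43 belongs to the 1-df accuracy test, for which n = 43 follows at .05.
- **Two tailed can be read sensibly.** On 1 df the upper-tail chi-square p-value equals the two-sided z-test p-value, so the phrase can simply mean non-directional at .05. This stands too. A reader might conclude that the rule is invalid, or that it also rejects for an unusually good fit to the null; nothing in the plan suggests that it was meant so.
- **Power is given as a floor.** With w = 0.62, 3 df and alpha .05, 43 patients give power .942, which satisfies the sentence. But section 10.5 describes a computation of required sample size, and that returns 37. No reason is given for going from 37 to 43.
- **A result below 50% would not support the section 10.2 alternative.** That is true, and a false claim of success from such a result is unlikely in practice. Still, the written rule does not exclude it, and one clause would.

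**Conclusion.** The point holds as a defect of specification and of one printed input. Section 10.5 does not reproduce from its own figures: at alpha .05 and w = 0.62 it should give 28, 33 or 37. On the two routes that do give 43, either the printed alpha or the printed w is wrong. The documents do not show which was entered in the power program, and .05 remains the only printed threshold. The primary test also lacks a null, degrees of freedom and a direction.

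It does not follow that the trial is too small: for the hypothesis in section 10.2, 43 patients give power .906 at alpha .05.

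The calculation rests on the noncentral chi-square approximation and, for the origin of w, on counting all 25 capsule-negative patients in the series as true negatives. The accuracy, sensitivity and specificity in section 10.5 imply that count. The correction should be made, but it changes neither the sample size nor the conduct of the trial.

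**What to change.** In sections 10.4.1 and 10.4.2, name one primary test that matches section 10.2. Suggested wording: *The primary test is a chi-square goodness-of-fit test with 1 degree of freedom, comparing the numbers of correct (TP + TN) and incorrect (FP + FN) capsule results with 50% each. The null is rejected if the upper-tail p-value is at most .05. This is equivalent to a two-sided test, and alpha is not halved. Success is claimed only if, in addition, observed accuracy exceeds 50%.* The exact binomial test should not be left as an open alternative, because it disagrees with the chi-square at 28/43.

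In section 10.5, replace w = 0.62 with w = 0.50 (75% against 50% accuracy), state 1 df and alpha .05, and report that 43 patients give power .906. This route is proposed because it agrees with section 10.2 and the printed alpha, not because the documents show that it was the one used.

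The cost is edits to three sections and one rerun of the power program, best done before capsule results are compared with endoscopy. The 43 evaluable and 50 enrolled patients stay as they are. The only downside is a corrected effect size in section 10.5.

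### On the reading that matches the stated null and N = 43, the uncorrected chi-square test of accuracy modestly exceeds .05 at both planned sizes (.066 at 43, .065 at 50); an exact binomial test restores control and keeps power above .90

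*Combined protocol and SAP*

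**What the plan says.** All of this is in the combined protocol and SAP; section 10.1 states that there is no separate SAP.

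- **Hypotheses (10.2).** "The assumed null hypothesis is that the accuracy of the HemoPill acute measurement in comparison with endoscopic finding is 50" per cent. For the alternative, "it is assumed that the accuracy is equal or higher to 75" per cent.
- **Test (10.4.1, repeated in 10.4.2).** A chi-square "goodness-of-fit test of a 2 x 2 contingency table with two tailed p-value of" .05. Neither section states the cells being compared, the degrees of freedom or a continuity correction. The only safeguard is a minimum expected cell size of 5.
- **Indices (10.4.2).** The four-way classification yields "calculated accuracy (ACC, = (TP + TN) / pop), sensitivity (true positive rate) and specificity (true negative rate"). Confidence intervals at 95% are mentioned as possible, with no method named.
- **Sample size (10.5).** "at least 43 eligible for statistical analyses", with 50 enrolled to allow for up to 14% dropout. The calculation used an alpha "error of .05 and a targeted power" "equal or higher than .90". The earlier study is said to "provide an accuracy of 75% (sensitivity of 100% and specificity of 63%) equaling an assumed effect size" w = 0.62.

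**The concern.** With 43 to 50 patients the number of correct calls takes few values near the critical region, so a chi-square approximation can have a true error rate some way from its nominal one. The usual rule of thumb on expected counts guards against sparse cells. It does not guard against this discreteness. If the test of the study's only formal hypothesis rejects more often than 5% under its own null, the stated alpha does not hold. A count on the boundary could then be declared significant when an exact test would not reject.

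**Working it through.** **Inputs.** Null accuracy .50 and alternative .75 (10.2); accuracy = (TP + TN)/N (10.4.2); two-sided alpha .05, power at least .90, 43 evaluable and 50 enrolled (10.5).

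**Step 1: reproduce N = 43.** For correct v incorrect calls, w = sqrt[(.75 − .50)²/.50 + (.25 − .50)²/.50] = 0.50. With df 1 the non-centrality is N × 0.25. Power is .8998 at N = 42 and .9064 at N = 43, so 43 is the smallest N reaching .90. The dropout step also reproduces: 43/(1 − .14) = 50.

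Other variants do not give 43 as the minimum at power .90: w = 0.50 with df 3 needs 57; w = 0.62 needs 28 (df 1), 33 (df 2) or 37 (df 3); a normal-approximation single-proportion formula needs 38.

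The printed 0.62 appears to have another origin. Section 2.1 reports 35 positive capsules, 20 of them confirmed, and 25 negative ones. Taken as 20/15/25/0 of 60 against 25% per cell, this gives w = sqrt(.3889) = 0.624.

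**Step 2: rejection rule of the uncorrected test.** Chi-square = (x − n/2)²/(n/4), critical value 3.841.

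- n = 43, x = 28: 6.5²/10.75 = 3.93, p = .047. At x = 27: 5.5²/10.75 = 2.81, p = .093. The rule rejects at 28 or more, or 15 or fewer.
- n = 50, x = 32: 7²/12.5 = 3.92, p = .048. The rule rejects at 32 or more, or 18 or fewer.

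**Step 3: exact size and power.** Size is 2 × P(X ≥ r) under Binomial(n, .5). Power is the probability of the rejection region under Binomial(n, .75). Here r is the smallest number correct that rejects in the upper tail.

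| n | Chi-square r | Size | Power | Exact r | Size | Power |
|---|---|---|---|---|---|---|
| 43 | 28 | .0660 | .9486 | 29 | .0315 | .9038 |
| 44 | 29 | .0488 | .9374 | 29 | .0488 | .9374 |
| 45 | 30 | .0357 | .9247 | 30 | .0357 | .9247 |
| 46 | 30 | .0541 | .9516 | 31 | .0259 | .9104 |
| 47 | 31 | .0400 | .9413 | 31 | .0400 | .9413 |
| 48 | 31 | .0595 | .9626 | 32 | .0293 | .9296 |
| 49 | 32 | .0444 | .9544 | 32 | .0444 | .9544 |
| 50 | 32 | .0649 | .9713 | 33 | .0328 | .9449 |

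**Step 4: the plan's safeguard.** Expected counts under the null are 21.5 per cell at n = 43 and 25 at n = 50. Both are far above 5, so the check passes while the size is above .05.

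**Step 5: other readings of the test.** Four cells against 25% each with df 3 has exact size .0487 at n = 43 and .0513 at n = 50. A Pearson test of independence has size of about .051 to .057, assuming endoscopy-positive prevalence of 33% to 50% and half of capsule results positive.

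**The case against.** **The plan may intend a different test.** Sections 10.4.1 and 10.4.2 speak of a 2 x 2 table with four outcomes, and w = 0.62 fits a four-cell comparison. With w = 0.62 and df 3, n = 43 has power .942, which also satisfies a target of at least .90. Under that reading, or under independence, the size is close to .05. This stands as a reason to make the finding conditional. It does not remove it, because neither alternative tests accuracy = 50%, the null in 10.2, and neither gives 43 as the required number.

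**The excess depends on the analysed n.** It is absent at 44, 45, 47 and 49. The unweighted mean size over 43 to 50 is .0517. If dropout from 50 is binomial, the average size is .0545, .0486 and .0497 at the dropout rates of 2%, 7% and 14% mentioned in 10.5. A reader might infer that the test generally fails to hold .05. The documents do not support that; the statement is confined to 43, 46, 48 and 50.

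**The p-value and interval need not conflict.** For 28/43 the Clopper-Pearson interval is 49.1% to 79.0% and includes 50%. The Wilson interval, which inverts this same chi-square test, is 50.2% to 77.6% and excludes it. A reader might infer that the plan contradicts itself here. It does not, because it names no interval method.

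**The exact test is conservative.** At n = 43 its size is further from .05 (1.85 points below) than the chi-square is (1.60 above), and the mid-p value for 28/43 is .049. That is true, but only the exact test guarantees that alpha is not exceeded.

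**Conclusion.** The concern holds conditionally and is minor. It assumes a two-cell, df 1, uncorrected test of accuracy against 50%, which is the reading that matches 10.2 and reproduces N = 43. On it, the stated alpha is exceeded by about 1.5 percentage points at both sizes the plan names.

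The practical reach is small. At n = 43 the chi-square and exact rules differ only at 28 correct calls and, symmetrically, at 15. Exactly 28 has probability 1.7% at 50% accuracy and 4.5% at 75%. It would be wrong to read this as invalidating the trial or its sample size: 43 evaluable patients still suffice under the exact test.

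The undefined cells and df, and the mismatch between w = 0.62 and N = 43, need settling whichever test the sponsor intends.

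**What to change.** - **10.4.1 and 10.4.2:** test accuracy = 50% with a two-sided exact binomial test at .05, and report the matching Clopper-Pearson 95% interval. This also removes the ambiguity over cells and df for the accuracy test.
- **10.5:** state the success rule (29 or more correct of 43; 33 or more of 50), the exact size (.032; .033) and the exact power at 75% accuracy (.904; .945). Replace w = 0.62 with the w = 0.50 that gives N = 43. If another n is analysed, the same test applies with the critical count for that n.

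A Yates correction is not an equivalent substitute. It gives the same rule as the exact test at 43 and 50, but at n = 44 its power is .887, below the .90 target.

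**Cost.** A few sentences and no extra patients. The success count rises by one at n = 43, 46, 48 and 50. Power falls from .949 to .904 at n = 43 and from .971 to .945 at n = 50, still above .90. The change should be made before the data are analysed, since altering the test once a boundary count is known would not be credible.

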### 10.4.2 Analysis of the Primary Efficacy Endpoint(s)

The original continues data level of the subject device, HemoPill acute, the so-called HI-value, is transformed during the study process by the investigator in dichotomous values, negative or positive for GI lumen bleeding, i.e. negative or positive output results (described in detail in section 2.1.2.2).

The qualitative visual data of the control product, the endoscopy, is also transformed during the study process by the investigator in dichotomous values, negative or positive for GI lumen bleeding, i.e. negative or positive output results (described in section 4.1).

After the study process the values of these two factors (HemoPill acute: negative or positive, endoscopy: negative or positive) are combined in a 2 x 2 contingency table with four possible results:

- True positive: HemoPill acute measurement positive; Endoscopy measurement positive
- False positive: HemoPill acute measurement positive; Endoscopy measurement negative
- True negative: HemoPill acute measurement negative; Endoscopy measurement negative
- False negative: HemoPill acute measurement negative; Endoscopy measurement positive

(for detailed description see section 4.1)

From this 2 x 2 contingency table the summary three test indices are calculated accuracy (ACC, = (TP + TN) / pop), sensitivity (true positive rate) and specificity (true negative rate).

The significance of these results will be analyzed using the  $\chi^2$  test, goodness-of-fit test of a 2 x 2 contingency table with two tailed p-value of  $\alpha \leq .05$ .

The data assumption of the  $\chi^2$  test, goodness-of-fit test, a required minimal expected cell size of 5, will be controlled. After the inference analysis the 95% confidence intervals of the test indices can be calculated. If either of both measurement results is missing for a patient, the whole subject is omitted from the data analysis.

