#### **10.4.9 Multiple Comparison/Multiplicity**

Not applicable.

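### Significance and .90 power are claimed for accuracy, sensitivity and specificity, but only accuracy has a null hypothesis and only accuracy is powered

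*Combined protocol and SAP*

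**What the plan says.** Four sections of the combined protocol and SAP bear on this, and section 10.1 says there is no separate SAP to settle it.

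- **10.2 Statistical Hypotheses:** "Formal hypotheses are only specified for the primary clinical effectiveness endpoint". The null is an accuracy of 50% and the alternative an accuracy of at least 75%. No value is given for sensitivity or specificity.
- **10.4.2 Analysis of the Primary Efficacy Endpoint(s):** accuracy, sensitivity and specificity are derived from the 2 x 2 table. The next sentence reads "The significance of these results will be analyzed using the" chi-square test, described as a "goodness-of-fit test of a 2 x 2 contingency table with two tailed p-value of" .05. It adds that 95% confidence intervals of the indices can be calculated afterwards.
- **10.4.9:** under "Multiple Comparison/Multiplicity" the plan answers that this does not apply.
- **10.5 Sample Size:** n = 43 was calculated for the planned chi-square "test for the test indices (accuracy, sensitivity and specificity"), with an alpha "error of .05 and a targeted power" that is "equal or higher than .90". The basis is a previous study "which provide an accuracy of 75% (sensitivity of 100% and specificity of 63%) equaling an assumed effect size" w of 0.62.

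No rule says which index, or how many, must be significant for the trial to succeed.

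**The concern.** The significance claim is extended to all three indices twice, in 10.4.2 and again in 10.5, so it is hard to dismiss as a loose pronoun. Neither way of carrying it out is sound.

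- **One test, one p-value.** The p-value answers a question about accuracy but would be reported as covering sensitivity and specificity, for which no hypothesis exists.
- **Three tests at .05.** Nothing controls the overall error. A trial whose accuracy test fails could still report a significant sensitivity or specificity.

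The wording matters because the hypothesis in section 2.3 is phrased as adequate sensitivity and specificity, so these are the indices that readers will quote. The power statement has the same problem: a reader of 10.5 would believe that specificity is tested with at least .90 power.

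**Working it through.** **Inputs.** From 10.2 and 10.5: two-sided alpha .05, power .90, n = 43, accuracy 75% against 50%, specificity 63%, w = 0.62. Assumed, because the plan gives no value: a null of 50% for sensitivity and specificity. The split of 43 patients into endoscopy-positive and endoscopy-negative is also not given. In the previous study described in 2.1, 20 of 60 patients had endoscopically confirmed bleeding, and one third of 43 is about 14, so 14/29 is used as the reference split and others are shown.

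**1. The plan's own sample size.** Power is taken from the noncentral chi-square with noncentrality n·w².

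- Accuracy 75% against 50%: w = √[(0.75 − 0.50)²/0.50 + (0.25 − 0.50)²/0.50] = √0.25 = 0.50. With 1 df, n = 43 gives noncentrality 43 × 0.25 = 10.75 and power 0.906. At n = 42 the power is 0.8998, so 43 is the smallest n that reaches .90.
- Stated w = 0.62: n = 28 suffices at 1 df (power 0.907) and 37 at 3 df. The figure 43 appears only at 5 df (power 0.901), which a 2 x 2 table does not have.
- A possible source of 0.62: cells of 20, 15, 25 and 0 out of 60 (true positive, false positive, true negative, false negative) set against four equal cells of 25% give w = 0.624. They also give accuracy 45/60 = 75%, sensitivity 20/20 and specificity 25/40 = 62.5%. That comparison is not a test of accuracy against 50%.

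So 43 fits the accuracy test, but not through the effect size that 10.5 reports.

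**2. Size of the accuracy test alone.** With the uncorrected chi-square at n = 43, rejection occurs at 15 or fewer or at 28 or more correct results. Under Binomial(43, 0.5) each tail has probability 0.0330, so the true size is 2 × 0.0330 = 6.6%.

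**3. Testing all three indices.** For D positives and 43 − D negatives, take TP ~ Binomial(D, 0.5) and TN ~ Binomial(43 − D, 0.5). Test TP/D, TN/(43 − D) and (TP + TN)/43 against 50%, and sum the probability of every outcome in which at least one is rejected. Accuracy is built from the other two counts, so the dependence is included.

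| Split (positive/negative) | At least one false rejection, uncorrected chi-square |
|---|---|
| 9/34 | 11.7% |
| 10/33 | 9.1% |
| 14/29 | 13.7% |
| 15/28 | 10.4% |
| 20/23 | 10.8% |
| 22/21 | 14.8% |

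Averaged over case counts for prevalences of 20% to 60%, the chi-square rate is 11.7% to 13.0%. With exact binomial tests it is 6.3% to 7.2%. The large-sample rate for prevalences of 20% to 50% is 11.2% to 11.5%.

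At 14/29, accuracy is not significant but sensitivity or specificity is in 13.7% − 6.6% = 7.1% of trials, counting both directions.

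**4. Power for specificity.** With 29 negatives, the chi-square rejects 50% at 9 or fewer or at 20 or more true negatives. Under Binomial(29, 0.63) that has probability 0.324, so power is about 32%.

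**The case against.** The best defence is that only one test is planned. Section 4.2.1 has a single primary endpoint, result accuracy. Section 10.2 confines formal hypotheses to it, and 10.4.1 and 10.4.2 describe one chi-square test of one 2 x 2 table. Secondary endpoints are only described, and no interim, subgroup or exploratory analysis is planned. On that reading there is one p-value, the nominal error is 5%, and the entry in 10.4.9 is correct. This reading is well supported, and it removes the error inflation. It does not remove the mislabelling: 10.4.2 and 10.5 still attach that p-value and its power to two further indices.

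A reader might instead infer a flat false-positive rate of about 14%, for example from 1 − 0.95³ = 14.26%. The documents do not support that. It needs three separate and independent tests, whereas accuracy is a function of the other two counts, and it needs null values for sensitivity and specificity that the plan never gives. The 13.7% at 14/29 is one split among several, and moving one patient to 15/28 gives 10.4%. Part of any excess over 5% is also the discreteness of the chi-square itself, since accuracy alone already has a size of 6.6%.

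It is also fair to say that intervals are already foreseen in 10.4.2, though only as something that can be done.

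**Conclusion.** The point holds as an inconsistency between 10.2 and 10.4.9 on one side and 10.4.2 and 10.5 on the other. Significance and .90 power are claimed for sensitivity and specificity without a hypothesis for either.

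Its size depends on the reading. With one test, the nominal error stays at 5% and the defect is one p-value presented as covering three indices. With three tests, the error is above 5%: about 9% to 15% with the uncorrected chi-square over the splits tried, and about 6% to 7% with exact binomial tests averaged over prevalence. Both ranges rest on an assumed 50% null for sensitivity and specificity.

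The .90 power claim fails for specificity, at about 32% under the plan's own 63%, an assumed 50% null and 29 negatives. It should not be inferred that n = 43 is too small for accuracy: it gives 0.906 there. Nor do the documents show that the original calculation was made for accuracy alone, because 10.5 names all three indices and reports w = 0.62.

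**What to change.** - **10.4.2 and 10.4.9:** name accuracy against 50% as the only significance test. State that sensitivity and specificity will be reported with exact 95% confidence intervals and without p-values. Put this statement in 10.4.9 in place of the present entry.
- **10.5:** remove sensitivity and specificity from the power statement and replace w = 0.62 with the calculation for accuracy 75% against 50%: w = 0.50, 1 df, alpha .05, n = 43, power about 0.91. Deleting two words is not enough, because the stated effect size does not lead to 43 for this test.

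Naming accuracy alone does not cure the 6.6% size of the uncorrected chi-square. If that matters to the sponsor, an exact binomial test at n = 43 rejects upward from 29 correct results, with two-sided size 2 × 0.0158 = 3.2% and power 0.904 at 75%.

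The cost is wording and one restated calculation. The targets of 43 evaluable and 50 enrolled are unchanged. The sponsor gives up p-values for sensitivity and specificity. If it wants to keep them, each index needs its own null value, a multiplicity rule and a new sample size; a Bonferroni split of .05/3 would already raise n for the accuracy test alone to 55.
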